- a. Latino day laborers participating in the Brief Motivational Intervention condition will report fewer hazardous exposures at work at post-test compared to the standard-of-care control group.
- b. Latino day laborers participating in the Group Problem Solving condition will report fewer hazardous exposures at work at post-test compared to the standard-of-care control group.

AIM 2 Determine the mediating effect of psychosocial stressors on VALES+Tú primary outcomes

Research question:

a. How do situational and immigration stressors mediate the impact of the intervention program on hazardous exposures at work?

The short-term goal of VALES+Tú is to reduce LDL exposures to workplace hazards by involving them in a corner-based safety program that effectively addresses situational and immigration related stress. These psychosocial factors are seldom targeted in safety programs but evidence indicates that they increase hazardous exposures at work. Our *long-term goal* is to reduce the high rates of injury in the Latino day laborer population. If successful, we will prepare VALES+Tú for future dissemination among LDL who look for work at day labor corners in other areas of the United States with large Latino enclaves.

Activities to be conducted prior to the start of the clinical Trial

I. Rapid Needs Assessment

Prior to the implementation of the clinical trial, we will also conduct a Rapid Needs Assessment (RNA). The purpose of the RNA is to gather information related to workers' current personal characteristics, work conditions, and injury experiences. Due to the amount of time that has elapsed since the culmination of the pilot study, conducting this rapid need assessment is a critical step in ensuring our clinical trial reflects current trends and dynamics among day laborers. The RNA will be conducted with LDLs at randomly selected corners. The assessment will be administered electronically by trained interviewers using iPads. The assessment will validate psychosocial and other measures used in our previous studies as well as newly developed items. The assessment will allow us to make any necessary adjustments to our study measures before conducting the clinical trial.

RNA participant selection and Recruitment:

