To explore the possibility that the effect of the intervention depends on certain other variables (i.e. moderation or effect modification), we will examine whether potential moderators statistically interact with the intervention condition, resulting in differential intervention effects. This is accomplished by adding a third term to the group by time interaction, creating a three-way interaction term. The multilevel model can accommodate moderators at the individual or cluster level (e.g. a cross-level interaction). Consistent with the FOA we are responding to, a moderator of particular interest is Latin American country of origin. Given the composition of the day labor pool in Houston, with a predominant Mexican population, we will examine country of origin as Mexico v. Central America. These methods are applicable for other potential moderators, like individual characteristics (e.g. demographic variables, anxiety, alcohol use) and characteristics of the street corners (e.g. size).

AIM 2 Determine the mediating effect of psychosocial stressors on VALES+Tú primary outcomes. To determine whether situational and immigration stress mediate the relation between the intervention and outcome (i.e. whether these variables "carry" the intervention effect), we will use cross-level

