mediation analysis, which accommodates a situation where the intervention is assigned at the cluster level, but the proposed mediator and the outcome are measured repeatedly over time. A conceptual model of the proposed analysis is shown in the figure below. We will use a version of the widely accepted product of coefficients methods with bias corrected bootstrapped confidence intervals, adapted for longitudinal designs with a randomized intervention assigned at the cluster level. The product of coefficients method has been shown to have greater statistical power than the Baron and Kenny causal steps method. In the three-level operationalization of mediation analysis, two models are specified: 1) A three-level model (street corners, individuals, and repeated measurements) with the mediator as the dependent variable and intervention condition, time and the intervention by time interaction (path a) as the predictors; and 2) a separate three-level model with the outcome (e.g. workplace hazards) as the dependent variable, and intervention condition, time, the mediator (treated as a time-varying covariate; path b), and the intervention by time interaction as predictors. The product of paths a (intervention effect to mediator) and b (mediator to outcome) from model 1 and model 2, respectively, is the mediated effect. Bootstrap resampling methods are then used to compute bias-corrected 95% confidence intervals for purposes of significance testing.

Ethics

IRB approval will be sought from CPHS. State whether IRB approval will be sought from CPHS or another IRB (under UT System Reciprocity Agreement).

Study personnel will explain the nature of the study and the benefits and risks of participating. LDL will be assured that they can pause the interview if they are offered a job and resume the interview later. Consent will be sought after this process, and eligible LDL wishing to participate will signify their consent by selecting the appropriate button presented on the iPad used to present the consent form.

Data handling and record keeping

Access to source documents will be limited to the Principal Investigator and other Key Personnel. Electronic records will be stored on password protected personal computers and on the University server. Records will be retained in accordance with applicable regulations. Paper records will be stored in locked cabinets.

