Participants will be assigned a unique study number. This number will be used to track data and other records. It will be necessary to collect names and contact information (including that for selected

friends and family) so that participants can be reached to schedule their follow-up interviews. This information will be stored in separated files and will be accessed on a need to know basis.

Surveys will be conducted using iPads. When not in use, iPads will be stored in locked cabinets. Completed surveys will be downloaded on a regular basis by the data manager.

Quality control and assurance

All data collection procedures and instruments will be pilot tested and revised as necessary. Computerized surveys will be programed to minimize out of range, inconsistent, or missing date.

The data manager will regularly audit data for problematic entries and provide feedback to the Principal Investigator and data collectors.

We do not have plans to employ third party monitoring.

Publication Plan

Manuscripts will be prepared for submission to relevant peer reviewed journals. Anticipated manuscripts will address participants' characteristics at baseline and the significance of changes in workplace injury and psychosocial items from baseline to follow-up within and between intervention groups.

We do not anticipate retuning results to participants.

ATTACHMENTS

- 1. Schematic of Study Design
- 2. Study Schedule
- 3. Consent Document
- 4. Case Report Form

COVID-19 Supplemental Study

Background and Rationale

The Vales+ Tu injury prevention study was awarded a supplemental grant from the National Institute on Minority health and Health Disparities (3R01MD012928-03S1). The purpose of the supplemental study is to assess the impact of the COVID-19 pandemic on Latino Day Laborers and their ability to adhere and implement COVID-19 mitigation practices.

LDL are routinely exposed to multiple interrelated stressors associated with both their work and their immigration status such as temporary work, crowded living conditions, and food insecurity. While the stressors are not new, they have been intensified by the COVID-19 pandemic as evidenced by their Latino's high COVID-19 mortality and morbidity rate.

Objectives

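### Aim 2 names two stress mediators but writes an outcome model for only one; if the stressors are correlated and the program lowers both, a stressor with no effect of its own can be declared a mediator

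*Combined protocol and SAP*

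**What the plan says.** Objectives, AIM 2 poses the question "How do situational and immigration stressors mediate the impact of the intervention program on hazardous exposures at work". Statistics, Analyses, AIM 2 repeats both mediators: "To determine whether situational and immigration stress mediate the relation between the intervention and outcome".

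The method is then written for one mediator:

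- "In the three-level operationalization of mediation analysis, two models are specified".
- Model 1 is a three-level model "with the mediator as the dependent variable and intervention condition, time and the intervention by time interaction (path a) as the predictors".
- Model 2 has the outcome as dependent variable. Its predictors are condition, time, "the mediator (treated as a time-varying covariate; path b), and the intervention by time interaction as predictors". The other stressor is not in the list.
- "The product of paths a (intervention effect to mediator) and b (mediator to outcome) from model 1 and model 2, respectively, is the mediated effect".
- Significance is judged from a bias-corrected 95% bootstrap interval for that single product.

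The AIM 2 text contains no model with both stressors, no second path b and no adjustment of one stressor for the other. It refers to a conceptual figure, which the available copy does not show.

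Three other places bear on the point. The short-term goal under Objectives has the program addressing both kinds of stress. The pilot results in Background Information report no significant reduction in either. The Background and Rationale of the COVID-19 Supplemental Study says "LDL are routinely exposed to multiple interrelated stressors associated with both their work and their immigration status".

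**The concern.** Applied as written, the pair of models runs once for situational stress and once for immigration stress. With only one stressor in model 2, its path b also absorbs whatever the omitted, correlated stressor does to hazardous exposures. If the program lowers both stressors and only one acts on exposures, the other still gets a non-zero product of paths and may pass the significance test.

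Aim 2 is one of two specific aims and asks how these two named stressors carry the effect. Single-mediator models cannot separate them, so a report of two mediators could describe one mechanism seen twice.

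**Working it through.** **Stated figure.** The documents give no power, sample size or error rate for Aim 2, so there is nothing to reproduce. The design inputs come from the Sample size paragraph, which concerns Aim 1.

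**Inputs from the documents.** 10 corners per condition, an average of 10 men per corner, ICC 0.02, across-time correlation 0.5, 30% attrition, and a 95% interval as the decision rule.

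**Assumed inputs.** Standardised stressors; situational stress acts on exposures with b = 0.30; immigration stress has b = 0; correlation r from 0 to 0.7; both stressors lowered by 0.3 to 0.5 SD. Corners are the bootstrap resampling unit. The roles of the two stressors can be swapped.

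**Step 1, the algebra.** With the inert stressor alone in model 2, its coefficient tends to

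b(alone) = b(active) × cov(active, inert) / var(inert) = r × 0.30.

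This gives 0.09, 0.15 and 0.21 at r = 0.3, 0.5 and 0.7. With a = −0.5 SD the apparent mediated effect is −0.045, −0.075 and −0.105 SD, when the truth is 0. The active stressor's true mediated effect is −0.5 × 0.30 = −0.150 SD. So the inert stressor is credited with 30%, 50% or 70% of it.

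**Step 2, change-score simulation.** 70 men per arm (100 less 30%), with Monte Carlo product intervals so that the bootstrap plays no part. Rate at which the inert stressor is declared a mediator, for both stressors lowered by 0.3 to 0.5 SD:

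| r | Alone in model 2 | Both in model 2 |
|---|---|---|
| 0.3 | 6–15% | 1–5% |
| 0.5 | 17–33% | 2–4% |
| 0.7 | 28–57% | 2–4% |

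**Step 3, closer to the planned procedure.** Three-level random-intercept model, one active arm against control (10 + 10 corners), bias-corrected bootstrap stratified by arm, 2,000 trials with 1,000 resamples each, two waves unless stated:

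| r | Fall in active / inert stressor (SD) | Alone | Joint |
|---|---|---|---|
| 0 | 0.5 / 0.5 | 10.4% | 10.0% |
| 0.3 | 0.5 / 0.5 | 46.0% | 10.1% |
| 0.5 | 0.3 / 0.3 | 48.2% | 6.6% |
| 0.5 | 0.5 / 0.5 | 78.0% | 9.7% |
| 0.7 | 0.5 / 0.5 | 89.1% | 9.8% |
| 0.5 | 0.5 / 0.25 | 40.2% | 5.0% |
| 0.5 | 0.5 / 0 | 10.2% | 1.6% |
| 0.5, three waves | 0.5 / 0.5 | 95.0% | 10.4% |

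At r = 0 the two approaches agree, which isolates the correlation as the cause. The simulated mean path b for the inert stressor alone is 0.09, 0.15 and 0.21, as in step 1, and about 0 jointly. Simulation error at 78% is √(0.78 × 0.22 / 2000) = 0.9 points. The rate of about 10% at r = 0 suggests that this bootstrap is itself liberal with 20 corners, which is a separate matter.

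**Step 4, the opposite causal order.** Suppose immigration stress raises situational stress, which raises exposures, and the program moves situational stress only through immigration stress. Immigration stress is then a genuine upstream mediator. In the change-score setting the single-mediator model detects it in 17–34% of trials (r = 0.5) or 30–57% (r = 0.7), and the joint model in 1–4%. The single-mediator rates are nearly the same as in step 2, so the data alone do not separate the two situations.

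**The case against.** - **The plan never says that the stressors are fitted one at a time.** That is inferred from the singular wording and the closed predictor list, and the missing figure might show both mediators. This stands as a caution. Even so, the written models are what would be programmed, and they hold one mediator.
- **A reader might infer that the documents report the trial's two stress measures as correlated.** They do not. The supplement sentence is general background on day laborers' stressors and gives no coefficient. Every r above is an assumption.
- **The scenario needs the program to move the inert stressor.** The pilot found no significant fall in either. With no movement the planned procedure gives 10.2%, about its own r = 0 rate, and the mean mediated effect is 0. Non-significance does not show that there is no effect, but the practical size is uncertain.
- **The inert stressor is also an assumption.** The Objectives section cites evidence that both stressors raise exposures. If both do, the result is an inflated effect, not a false mediator.
- **A reader might conclude that only the joint model counts.** Step 4 shows why not: under a causal chain, mutual adjustment removes a real mediator. The documents state no causal order. This objection stands in full and shapes the fix.
- **Two consequences are not supported.** No section says that Aim 2 decides which stressor later programs target. Nor does the plan add the two mediated effects. If someone did, the sum with equal a paths would be (1 + r) times the true total, or 1.5 times at r = 0.5.

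**Conclusion.** The point holds as a gap in the specification with a real error attached. Two mediators are named, and the written outcome model admits one. Under correlated stressors that both move, an inert stressor is declared a mediator in about 6–15%, 17–33% or 28–57% of trials (r = 0.3, 0.5, 0.7) in the change-score setting. It happens more often in the three-level model with the bias-corrected bootstrap: 48–78% at r = 0.5, against 7–10% jointly.

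These sizes rest on assumed values for r, for path b and for the falls in stress. The excess largely vanishes if the inert stressor does not move. The documents do not support saying that Aim 2 will name the wrong mediator, or that the joint model is correct whatever the causal order. They support adding a joint analysis beside the single-mediator one. The change should be made, with medium confidence.

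**What to change.** In Statistics, Analyses, AIM 2:

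1. Fit model 1 to each stressor separately, giving a1 and a2.
2. Add an outcome model with both stressors, giving mutually adjusted b1 and b2.
3. For each arm against control, report a1 × b1, a2 × b2 and their sum, beside the single-mediator effects. Report the correlation between the stressors.
4. Base any claim that one stressor mediates independently of the other on the joint model. Describe single-mediator effects as unadjusted, and do not add them together.
5. State that the joint model assumes neither stressor causes the other. If the two analyses disagree, report the attribution as unresolved.

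If a joint model is already intended, one clarifying sentence covers step 2.

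**Cost.** A few lines of text and one more covariate; no new data. Intervals for the specific effects widen when r is high. In the change-score model with a = 0.5, power for the true mediator falls from 77% to 73% at r = 0.5 and from about 80% to about 60% at r = 0.7. The three-level simulation showed no material loss (88.8% alone against 89.7% jointly at r = 0.5; 89.2% against 88.9% at r = 0.7). The joint result also depends on the no-causal-order assumption and does not remove confounding by unmeasured factors.

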Corner selection and assignment. Our recent corner needs assessment study mapped 44 corners in the Houston area bounded by the Sam Houston Tollway, covering about 350 square miles. We will base our sampling design on that number and distribution, and, prior to implementation we will survey corner sites to confirm their stability and identify new corners that may have emerged using the methodology of our Phase I pilot study. The Workers Center Outreach Coordinator will be responsible for visiting and mapping the corners. A "corner" is a) a labor hiring public location such as a street corner, bus stop, gas station or home improvement stores within the designated geographic area, b) an independent hiring site (independence as defined by at least 3 blocks of physical distance from the nearest corner), and c) a hub for day laborers observed seeking employment at that location. Locally, corners range in size from quite small (5 to 10 men) to very large (> 75 men), with the majority

supporting 12 to 30 LDL looking for work on a given day. To reach our enrollment goal of a total of 300 LDL, we plan to randomly sample 30 corners from the total number identified and select an average of 10 LDL at each corner to enroll in the study. As corner sizes vary, we may enroll fewer LDL at some corners than at others. The number of corners/clusters sampled will be kept to the sampling design of 10 per group (total of 30) to maximize statistical power.

Sample size. Sample size was estimated using Monte Carlo simulation procedures. For purposes of the simulation, we made the following assumptions: a cluster randomized design, an intervention condition at the cluster (i.e. street corner) level, 20 interventions corners, split equally across the two intervention conditions, 10 control corners, an intraclass correlation coefficient (ICC) of 0.02, an across-time correlation of outcome measures of 0.5 (derived from our pilot data), a nominal alpha of 0.05, desired power of at least 80%, three measurement waves (one pre-test and two post-test), and attrition between baseline and wave 3 of 30%. A group by time interaction serves as the primary indicator of treatment effect, with a minimum desired detectable interaction parameter estimate of 1.5 units (a value also derived from our pilot data) on the workplace hazards scale. Based on these parameters, we require an average of 10 participants from each of the 30 corners, for a total of 300 participants at baseline.

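### If corners are resampled, the Aim 2 bias-corrected bootstrap test rejects in about 8-11% of trials, not 5%, when one mediation path is zero and the other is moderate

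*Combined protocol and SAP*

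**What the plan says.** The AIM 2 text under Statistics, Analyses fits two three-level models. One has the mediator as outcome and gives path a, the intervention-by-time effect. The other has hazardous exposures as outcome, with the mediator as a time-varying covariate, and gives path b. "The product of paths a (intervention effect to mediator) and b (mediator to outcome) from model 1 and model 2, respectively, is the mediated effect".

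The plan uses a version of the "product of coefficients methods with bias corrected bootstrapped confidence intervals", described as "adapted for longitudinal designs with a randomized intervention assigned at the cluster level". The interval is also the test: "Bootstrap resampling methods are then used to compute bias-corrected 95% confidence intervals for purposes of significance testing".

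The plan does not give the resampling unit, the number of resamples, a small-sample correction, or any check of the error rate for this interval. The Monte Carlo work under Sample size covers only the Aim 1 group-by-time effect.

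Corner selection and assignment fixes 10 corners in each of the three groups, and Sample size states: "we require an average of 10 participants from each of the 30 corners, for a total of 300 participants at baseline". The AIM 1 text compares each intervention arm separately with the common control.

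**The concern.** A bootstrap that resamples few clusters understates variance and takes no account of the heavier tails of a small-sample statistic. For a product of two paths, the bias correction also moves the limits outward from the resampled distribution in a way that favours rejection when one path is zero. With 10 corners per arm, the two effects act together.

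The setting where this matters is one the protocol makes plausible. The Pilot test section reports no statistically significant fall in immigration or situational stress, so a path a near zero is possible. The Objectives section says that these stressors raise exposure to hazards, so path b is expected to be non-zero. A false finding of mediation would credit stress reduction as the working mechanism. That is how the short-term goal is framed, and dissemination is planned if the programme succeeds.

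**Working it through.** **The plan's own figures.** The only design figure is 30 corners x 10 = 300 participants, derived for Aim 1. No power, error rate or coverage is given for Aim 2 beyond the nominal 95%, so there is no Aim 2 figure to reproduce.

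**Inputs from the documents.** 10 corners per arm; 10 participants per corner; ICC 0.02; across-time correlation 0.5; 30% attrition (represented as 7 per corner). Sample size assumes three waves while Study Procedures describes one follow-up at one month, so two and three waves were both run.

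**Assumptions.** Whole corners are resampled within arm, with 1,000 resamples. The documents give no path sizes, so a and b are ranges in SD units. Variance components were held at their true values.

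**Why few corners alone inflate the error.** If b is clearly non-zero, the product test becomes in effect a test of a. Resampling K corners within an arm gives a variance too small by (K - 1)/K = 9/10 = 0.9. The effective critical value is about 1.96 x sqrt(0.9) = 1.86. The correct value is t with 10 + 10 - 2 = 18 df, which is 2.10. The two-sided tail of t(18) beyond 1.86 is about 7.9%. That is close to the simulated percentile figures of 8.1-8.5% at b = 0.3-0.5 below.

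**What the bias correction adds.** With z0 the normal quantile of the share of resampled products below the estimate, the limits are taken at the percentiles Phi(2*z0 - 1.96) and Phi(2*z0 + 1.96) rather than at 2.5% and 97.5%.

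**Rejection of a true null (%), random-intercept model, two arms, two waves, 10 per corner, 4,000 trials per row** (Monte Carlo SE about 0.3-0.5 point). The last two columns are from a separate run of the same design, with a corner-based standard error and t(18) for path a and a model-based standard error for path b.

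| a | b | Bias-corrected | Percentile | Joint test | Monte Carlo interval |
|---|---|---|---|---|---|
| 0 | 0 | 1.3 | 0.3 | 0.3 | 0.1 |
| 0 | 0.05 | 3.7 | 1.6 | not run | not run |
| 0 | 0.10 | 8.3 | 4.5 | 2.6 | 2.2 |
| 0 | 0.20 | 9.9 | 7.2 | not run | not run |
| 0 | 0.30 | 10.0 | 8.5 | 4.9 | 5.0 |
| 0 | 0.50 | 8.7 | 8.1 | 5.3 | 5.4 |
| 0.2 | 0 | 4.7 | 2.2 | 1.6 | 1.1 |
| 0.4 | 0 | 10.2 | 6.1 | 4.1 | 3.5 |
| 0.6 | 0 | 11.3 | 8.7 | 4.8 | 4.6 |

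**Sensitivity.**
- With three arms, three waves, or a corner-by-time variance of 0.02, the bias-corrected test rejects in 8.0-11.0% once the non-zero path is b >= 0.10 or a >= 0.4.
- With 7 per corner it rejects in 5.9% at b = 0.10 and 8.7-10.7% at larger paths.
- A simpler change-score simulation (7 per corner, ICC of change 0.02, 4,000 data sets) gives 9.7%, 10.8% and 10.3% at a = 0 with b = 0.2, 0.3 and 0.4, and 8.3% at a = 0.4 with b = 0.
- The point b = 0.10 is transitional: change-score runs give 4.4-4.6% there, against 8.3% in the table.

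**Power at a = 0.4, b = 0.3 SD.** Bias-corrected 68%, percentile 60%, joint test or Monte Carlo interval 47-51%.

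**The case against.** The strongest objection is that the excess is conditional. A reader might infer that the Aim 2 intervals are too narrow under any null. The table does not support that: with both paths zero, rejection is 1.3%, and with a weak non-zero path it is mostly below 5%. This objection stands, and it limits the claim to one zero path with the other moderate.

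Second, the plan never says that corners are resampled. That also stands; it is a reading, though the natural one for a method said to be adapted to cluster assignment. Resampling participants is not a reliable escape. With no corner-level variance in change it rejects in 0.7-8.2%, mostly 4-8%. With an ICC of change of 0.02 or 0.05 (a = 0, b = 0.3, 10 per corner), it rejects in 11.0% or 14.8%. Other multilevel bootstraps were not examined.

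Third, the bias correction might be blamed for everything. It is not the sole cause: it adds 0.6 point at b = 0.5 and 4.1 points at a = 0.4 in the table. Dropping it alone would not restore 5%.

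Fourth, a reader might take the pilot as proof that path a is zero. It had 75 pretest participants and one corner per condition, and a non-significant result there shows only that a zero path is plausible.

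Last, Aim 2 is posed as a research question without a hypothesis, and the Aim 1 tests are untouched. That limits the consequence. But Aim 2 is one of two specific aims, and the plan uses this interval for significance testing.

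**Conclusion.** The concern holds in conditional form. With 10 corners per arm in each contrast and corner-level resampling, the planned test rejects in about 8-11% of trials instead of 5% when one path is zero and the other is moderate (b about 0.2-0.4 SD, or a about 0.4 SD). It is conservative, at about 1-5%, when both paths are zero or the non-zero path is weak. The cause is few corners together with the bias correction.

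The result rests on assumed path sizes, on the unstated resampling unit, and on simulations that held variance components at their true values or used change scores. It held across two and three waves, two and three arms, and 7 or 10 participants per corner. The documents do not support a general statement that the 95% intervals are too narrow, nor any doubt about Aim 1 on this ground.

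**What to change.** In the AIM 2 analysis text, replace the bias-corrected bootstrap as the significance test. Suggested wording:

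*Mediation will be tested by joint significance of paths a and b [or by a Monte Carlo distribution-of-product 95% interval], using corner-based standard errors and a t reference with about 18 degrees of freedom for path a in each arm-versus-control contrast. Any bootstrap interval will resample whole corners within arm and will be reported as supportive.*

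Choose one of the two tests in advance. A percentile bootstrap should not take the place of the test, because it still rejects in up to about 8-9%.

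The change is a sentence or two of text and needs no new data. The cost is lower apparent power for mediation: about 68% to 47-51% at a = 0.4, b = 0.3 SD. Part of that difference is the inflated error and not real sensitivity.
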